Anyone in the study who tests positive for COVID-19 as part of the study (both Index Participants and Network Contacts) will be eligible for the CloseST study: a cohort study of individuals with COVID-19 infection. They will be offered additional test kits or clinic test referrals based on which study arm they were initially assigned. They will then be encouraged to get their close contacts tested as well. After the transition to Ellume test kits (planned for the start of December, 2021), we will no longer be able to monitor test results from self-testers. Self-testers who test positive must contact study staff to be enrolled in the study.

Figure 1: Overall study plan:

Study Sites:

This study will be conducted at three clinic sites across Philadelphia in the Public Health Management Corporation network.

PHMC Care Clinic – FQHC that focuses on serving people with HIV, viral hepatitis, and substance use disorders. Currently this study site provides COVID-19 testing mostly by appointment. Some walk-ins are allowed.

[name]
[name]

Congreso Health Center – FQHC that provides primary care to predominately Spanish-speaking population in North Philadelphia. Currently this study site provides outdoor COVID-19 testing by appointment only. Staff are expected to be fluent in Spanish and English.

[INACTIVE STUDY SITE]
[name]
[name]

Health Connection – FQHC

[name]
[name]

Rising Sun – FQHC

[name]
[name]

Mary Howard Health Center For The Homeless – FQHC that focuses on providing care to people who are experiencing homelessness. There is currently no study Interviewer carrying out recruitment activities at this clinic.
[INACTIVE STUDY SITE]

Table of Contents:

Manual of Procedures (MOP) is broken up into the following sections:

OVERVIEW OF STUDY

INDEX PARTICIPANTS

- a. Initial Recruitment
- b. Eligibility and verbal informed consent
- c. Baseline survey
- d. Testing and signed informed consent
- e. Randomization
- f. Intervention
- g. Study compensation
- h. Delivery of test results
- i. 8-week follow-up and study compensation

NETWORK CONTACTS

Self-test arm

- a. Informed consent and registration
- b. Home testing
- c. Delivery of test results

Test referral arm:

- a. Verbal informed consent and registration
- b. Signed informed consent
- c. Clinic test
- d. Delivery of test results

TEST RESULTS

MANAGEMENT OF POSITIVE COVID-19 TEST RESULTS

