APPENDIX DOCUMENT: STUDY SCRIPTS

APPENDICES: SOPs

[SOP: Rising Sun](#)

[SOP: Health Connection](#)

[SOP: EPIC EHR](#)

[SOP: Ellume test kit labels](#)

[SOP: Index Participant recruitment](#)

[SOP: Required baseline survey questions](#)

[SOP: Tracking referral IDs](#)

[SOP: Participant Payments](#)

[SOP: Follow-up surveys](#)

[SOP: Network Contacts](#)

[SOP: Recruitment Tracker](#)

OVERVIEW OF STUDY

Trial Design

The C-STRAND study is a 1:1 randomized control trial randomizing participants to receive either multiple self-collection test kits or multiple referrals for clinic-based tests to distribute within their social networks. These individuals, called *Index Participants*, will be encouraged to distribute self-collection test kits or test referral cards to others in their social networks, called *Network Contacts*. Network Contacts can include household members, friends, family, colleagues, or others in Index Participants' social networks. We will evaluate COVID-19 test uptake among Network Contacts.

To achieve our second aim, the CloseST study is a cohort study of both index participants and network contacts diagnosed with COVID-19 from the C-STRAND trial. Participants will then receive additional self-collection test kits or referrals for clinic-based tests to distribute to close contacts, based on their treatment assignment group from the C-STRAND trial. We will compare test uptake among close contacts of individuals with COVID-19.

Allocation

In the C-STRAND trial, we will use permuted block randomization with varying block sizes stratified by study site to assign Index Participants to receive multiple self-collection test kits or multiple referral cards for standard clinic-based tests. Investigators will have access to arm assignment on a need-to-know basis only, but participants and research assistants will not be masked with respect to study arm.

For the CloseST study, Index Participants and Network Contacts who test positive will be assigned to the intervention arm (receiving multiple self-collection test kits) or control arm (test referrals) according to their original assigned arm in the C-STRAND trial.

Intervention

Secondary distribution of COVID-19 self-collection test kits

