In order to link Network Contacts who obtain COVID-19 tests to Index Participants, each Index Participant will be assigned a Referral Identification (ID) number. This number will appear on all test referral cards and text messages in the control group, and on test kits in the intervention group. When network contacts request testing, they will be asked to provide the Referral ID number linking them to the Index Participant. We will measure test uptake among self-testers through testing completed at the partner self-testing lab. Among facility-based testers, test uptake will be measured through testing at one of the clinic sites. Study personnel will communicate all test results back to study participants via telephone, with an electronic copy of test results available upon request.

Outcomes

The primary outcome in the C-STRAND trial is the proportion of Index study participants linked to at least two Network Contacts who completed testing. Secondary outcomes at the end of the follow-up (week 8) and end of the study by each arm include: number of contacts tested, number of network contacts who test positive, test positivity rate and proportion of first-time test takers. All of these outcomes will be assessed with collected testing results and not rely on self-reported measures. Baseline and follow-up surveys will provide self-reported outcomes related to socio-demographic characteristics as well as COVID-19 exposure, symptoms, testing, and vaccine acceptance.

For the CloseST study, the primary outcome is the number of close contacts who test positive in each group.

Secondary outcomes at the end of the follow-up (week 8) by each group, include number of contacts tested and number of new cases identified. Similarly, baseline surveys of network contacts in the cohort study will provide similar self-reported outcomes as in aim 1.

[figure not shown]
INDEX PARTICIPANTS

Index participants are the study participants that we are enrolling in our primary study. They are adults who are seeking care at one of the three PHMC sites, and we are aiming to recruit them to then distribute home test kits or clinic test referrals to their contacts.

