For the CloseST study, we will aim to recruit up 210 study participants in the C-STRAND trial diagnosed with COVID-19. Data from the Philadelphia Department of Public Health shows that the median number of close contacts provided per individual with COVID-19 is approximately three.²¹ Assuming the mean number of close contacts *infected* with COVID-19 is approximately one, and 50% obtain testing, we can expect the mean number of positive tests per index COVID-19 positive index participant to therefore be approximately 0.5. We assumed a conservative allocation ratio of 2:1 and estimated the standard deviation of the number of positive tests in the network of COVID-19 positive index participants to be between 0.6 and 0.8. We considered a doubling from 0.5 to 1.0 new cases identified per positive index to be clinically significant. At the low end of the standard deviation range, we would need a total N=54 for 80% power with a p=0.05. With a standard deviation as high as 1.0, we would need a total N=192 to have 90% power to detect a difference between groups. A total of 210 individuals (representing a 20% positivity rate among Index Participants), even with a standard deviation of 1.0, would give us 93% power to detect a doubling of positive cases identified.

Data Analysis

All analyses will be performed based on intention-to-treat. In the C-STRAND trial, the primary analysis will use the Cochran-Mantel-Haenszel test, adjusting for study site, to compare the proportion of individuals in each arm who succeeded in getting two contacts tested. Sex will be included with an interaction term in multivariable models using logistic regression. In secondary analyses, Wilcoxon Rank-sum tests and linear regression or negative binomial regression will be used to compare each of the count and continuous outcomes (e.g., total number of contacts tested).

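### Site is a randomization stratum and enters the primary test, but the C-STRAND secondary count and continuous analyses name no site term; power is lost only if site predicts the outcome

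*Combined protocol and SAP*

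**What the plan says.** Under Allocation the plan states that "we will use permuted block randomization with varying block sizes stratified by study site". Under Data Analysis, "the primary analysis will use the Cochran-Mantel-Haenszel test, adjusting for study site". So site is used both in the randomization and in the primary test.

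The secondary outcomes listed under Outcomes are "number of contacts tested, number of network contacts who test positive, test positivity rate and proportion of first-time test takers". For those that are counts or continuous, the same Data Analysis paragraph says that "Wilcoxon Rank-sum tests and linear regression or negative binomial regression will be used". Site is not mentioned for any of these methods, and the plan does not say whether the rank test or the regression is the main analysis.

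Site of recruitment appears once more, at the end of Data Analysis. There it is one of several possible confounders for the CloseST cohort, to be considered only if imbalance is seen. That sentence does not cover the C-STRAND secondary outcomes.

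**The concern.** Blocked randomization within site balances the arms within each site, so differences between sites contribute almost nothing to the observed difference between arms. A plain rank-sum test still counts the between-site spread as noise. If sites differ in uptake, its standard error is too large, its p-values tend to be too large, and real differences are missed more often than they need be.

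A rank-sum test takes no covariates, so as named it is unstratified. The regressions could carry site, but the plan does not say that they will. The secondary results would then follow a different adjustment from the primary result. Whether site enters the regressions would also be open to choice after the data are seen.

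**Working it through.** **1. The plan's own figure.** The only C-STRAND sample size is for the primary outcome (Sample Size): 45% in the control arm, a 10-point difference, two-sided 0.05, 90% power. For 45% v 55%, with pooled variance under the null:

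n per arm = [1.960·√(2·0.5·0.5) + 1.282·√(0.45·0.55 + 0.55·0.45)]² / 0.10² = (1.3859 + 0.9017)² / 0.01 = 523.3, rounded up to 524, so 1048 in total.

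This matches the plan. No power, standard deviation or site-level rate is given for the secondary outcomes, so everything below rests on assumptions.

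**2. Formula.** Let R² be the share of the variance of the ranks that site explains. With balance within site, the plain rank-sum statistic has null variance of about 1 − R² instead of 1. Let d = 1.96 + z(power of the stratified test). Then:

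- type I error = 2·[1 − Φ(1.96/√(1 − R²))]
- power of the plain test = 1 − Φ(1.96/√(1 − R²) − d)

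Example with R² = 10% and stratified power 80%: 1.96/√0.90 = 2.066, so type I error is 0.039. With d = 1.96 + 0.842 = 2.802, power = Φ(2.802 − 2.066) = Φ(0.736) = 76.9%.

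| R² (assumed) | Type I error, plain test | Plain power if stratified is 70% | if 80% | if 90% |
|---|---|---|---|---|
| 0% | 0.050 | 70.0% | 80.0% | 90.0% |
| 2% | 0.048 | 69.3% | 79.4% | 89.7% |
| 5% | 0.044 | 68.2% | 78.5% | 89.1% |
| 10% | 0.039 | 66.2% | 76.9% | 88.0% |
| 20% | 0.028 | 61.5% | 72.9% | 85.3% |
| 30% | 0.019 | 55.6% | 67.7% | 81.6% |

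**3. Simulation at moderate power.** Assumptions: about 1048 index participants, three equal sites, 1:1 within site, beta-binomial counts of 0 to 5 (five kits or cards each), within-person correlation about 0.3, and a 1.15-fold gain. The rows come from separate runs, so read across a row and not down a column. With 4,000 trials, the Monte Carlo standard error near 70% is √(0.7·0.3/4000), or about 0.7 points.

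| Site uptake (assumed) | R² | Power, plain | Power, van Elteren |
|---|---|---|---|
| equal | about 0 | 69% | 68% |
| 26/31/36% | about 2% | 70.1% | 70.7% |
| 21/31/41% | about 7% | 66.0% | 69.5% |
| 15/31/47% | about 18% | 63% | 72% |
| 10/30/60% | about 36% | 59% | 81% |

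Type I error, plain v van Elteren, was 3.0% v 4.6% in the fourth row and 1.1% v 4.8% in the fifth.

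**4. Simulation at the plan's own planning effect.** Here the effect was set so that, with equal sites, about 45% v 55% of index participants have at least two contacts tested. Power, plain v van Elteren, was:

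- no site effect: 96.8% v 96.8%
- R² about 2%: 96.6% v 96.8%
- R² about 9%: 95.1% v 96.0%
- R² about 24%: 91.1% v 95.5%

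When power is this high, even a strong site effect costs only about 4 points.

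**The case against.** The strongest reply is that the documents do not show that sites differ in the number of contacts tested, so the loss may be nil. That stands: the effect is conditional.

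A reader might infer site differences from the Study Sites section, for example from the centre with a predominantly Spanish-speaking population. That centre appears to be marked inactive, and Eligibility Assessment names Health Connection, Rising Sun and Care Clinic as the recruiting sites. Among these, only Care Clinic is described as serving a particular population, and only Rising Sun is said also to recruit vaccine patients and new patients actively. These facts make some difference plausible. None of them gives its size.

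A reader might also take a loss of 10 to 20 points as the expected cost. That needs strong assumptions. With the counts modelled as in step 3, uptake of 15/31/47% means that about 20/43/64% of index participants at the three sites reach the primary endpoint, and 10/30/60% means about 13/42/78%.

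Finally, the plan does not say that site is excluded. It is silent, and the regressions it names could include site. That is also correct, so the omission concerns the secondary analyses as a group and not a deliberate choice of an inferior test. It does not rescue the rank-sum test, which cannot take a site term unless it is replaced by its stratified form.

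**Conclusion.** The point holds as a low-severity one. The randomization and the primary test use site, while the C-STRAND secondary count and continuous analyses do not name it. If site predicts the outcome, the plain rank-sum test is conservative. The loss is nil with similar sites, under about 1 point at R² of 2% or less, and about 1 to 4 points at 5–10%. It is about 10 points or more only when site explains roughly 20% or more and stratified power is about 70–80%. These sizes rest on assumed R², equal site shares and an assumed count distribution. They were worked out for the rank test and not for the negative binomial model.

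Three stronger readings are not supported:

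- **False positives.** The error is in the conservative direction, so false-positive control is kept.
- **The primary result.** The primary test already adjusts for site.
- **A main secondary outcome.** The plan lists its secondary outcomes without ranking them and gives the total number of contacts tested only as an example.

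**What to change.** In Data Analysis, replace the rank-sum test with the site-stratified Wilcoxon (van Elteren) test. State that the linear or negative binomial model for each C-STRAND count or continuous secondary outcome includes site indicators. Define the strata as the sites used in the randomization, including any site that enrolled participants and later became inactive. The same sentence can say whether the rank test or the regression is the main analysis for each outcome.

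The cost is a line or two of text. No new data are needed, the sample size does not change, and the equal-site simulations show no loss of power beyond Monte Carlo error. The secondary analyses would then follow the same strata as the randomization and the primary test.

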After confirming eligibility and completing informed consent, individuals in the control arm will complete a baseline survey. Thereafter, they will receive five test referral cards at study enrollment to offer free, facility-based COVID-19 testing at clinic sites for their network contacts. Participants will be encouraged to distribute referrals to individuals in their social network who are symptomatic, have a known exposure to COVID-19, or are otherwise at high risk for COVID-19 due to potential exposures. Each referral card will be assigned a unique referral number associated with the index participant. The index participant will be provided a text message with instructions that can be disseminated to his social network along with the referral cards. Test results will be released via phone call by study staff, and a paper or electronic copy of test results will be available upon request. Consistent with public health authority guidelines, multiple efforts will be made to contact participants with positive results. Each individual will be offered follow-up care and counseling. Index participants will be asked to complete an online follow-up survey after 8 weeks.

Follow-Up

Index participants and network contacts who test positive for SARS-CoV-2 and provide verbal informed consent for the cohort study will have baseline surveys completed online or through phone. Index participants and network contacts from the treatment arm (exposed group) will be offered 3 additional self-collection test kits to distribute to close contacts. Index participants and network contacts from the control arm (unexposed group) will be offered 3 additional test referral cards to be distributed to close contacts. Test results will be released via phone call by PHMC staff. Each individual will be offered follow-up care and counseling by clinical providers of PHMC.

Measuring COVID-19 test uptake

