In the CloseST study, we will use Poisson regression to compare the number of contacts who test positive at week 8 among contacts of SARS-COV-2 positive individuals who received the intervention or the control. Additional comparisons will follow the same approach for the secondary outcomes. Standardized mean differences (SMDs) > 0.1 will be used to determine balance between arms and identify potential confounders between participants in either study arm. If there is imbalance in the characteristics between the arms, additional analyses will consider potential confounders, including age, race/ethnicity, education, employment status, socioeconomic status, housing status, household size, relationship status, risk of COVID-19 exposure, and site of recruitment.

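### The CloseST primary Poisson regression names no variance estimator; with ordinary Poisson errors the 5% test would have size of about 2% to 8% over the planned SD range at mean 0.5

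*Combined protocol and SAP*

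**What the plan says.** The CloseST primary outcome (Outcomes section) is the number of close contacts who test positive in each group. For its analysis the Data Analysis section states: "we will use Poisson regression to compare the number of contacts who test positive at week 8 among contacts of SARS-COV-2 positive individuals". Secondary outcomes are to follow the same approach. No standard error method, dispersion allowance, fallback model or treatment of linked participants is given. For C-STRAND secondary outcomes, the same section does offer a model with a dispersion parameter: "linear regression or negative binomial regression will be used to compare each of the count and continuous outcomes".

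The Sample Size section expects a mean of about 0.5 positive tests per COVID-positive participant and looks for a doubling to 1.0. It sets the spread separately: the investigators "estimated the standard deviation of the number of positive tests in the network of COVID-19 positive index participants to be between 0.6 and 0.8". It adds a stress value: "With a standard deviation as high as 1.0, we would need a total N=192" for 90% power.

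On who enters CloseST, the Overview says "Anyone in the study who tests positive for COVID-19 as part of the study (both Index Participants and Network Contacts) will be eligible". The Allocation section places them "according to their original assigned arm in the C-STRAND trial". The Follow-Up section says "Index participants and network contacts from the treatment arm (exposed group) will be offered 3 additional self-collection test kits to distribute to close contacts", with a matching offer of referral cards in the control arm.

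**The concern.** The sample size treats the SD as a free quantity. Poisson regression with ordinary errors does not: it fixes the variance at the mean. The study may therefore be sized under one variance assumption and tested under another. If the true SD is below the Poisson value, the interval for the primary comparison is too wide; if it is above, the interval is too narrow and the p-value too small. Because the plan names no estimator, the choice between ordinary and robust errors could also be made after the data are seen.

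A secondary matter is independence. An Index Participant and that person's own positive Network Contacts can all enter CloseST, always in the same arm. Positive correlation among them would make unclustered errors too small.

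**Working it through.** **Inputs, all from the Sample Size section.** Means 0.5 and 1.0; SD 0.6 to 0.8, stress value 1.0; allocation 2:1; N = 210; alpha 0.05. Two-sided testing is my assumption, since sidedness is not stated for CloseST.

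**The plan's own figures.** For two means with common SD and 2:1 allocation, the smaller group is n = 1.5 × (z₀.₉₇₅ + z_power)² × SD² / 0.5².
- SD 1.0, 90% power: 1.5 × 10.51 × 1 / 0.25 = 63.04, so 64 and a total of 192. The plan says 192.
- SD 0.6, 80% power: 1.5 × 7.849 × 0.36 / 0.25 = 16.95, so 17 and a total of 51. The t-based calculation gives 54, the plan's figure.
- N = 210 (70 and 140), SD 1.0: SE = √(1/70 + 1/140) = 0.1464; 0.5 / 0.1464 − 1.96 = 1.456; power 92.7%. The plan says 93%.

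So the planning is a comparison of means with one SD for both arms, not tied to the mean.

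**Size with ordinary Poisson errors.** Under a common mean μ, the model-based variance of the log rate ratio is (1/μ)(1/n₀ + 1/n₁). The true variance is (SD²/μ²)(1/n₀ + 1/n₁). Their ratio is φ = SD²/μ. The size is 2 × (1 − Φ(1.96/√φ)), and the ordinary interval is 1/√φ times the correct width.

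| SD at μ = 0.5 | φ | Size | Width ratio |
|---|---|---|---|
| 0.6 | 0.72 | 2.1% | 1.18 |
| 0.7 | 0.98 | 4.8% | 1.01 |
| 0.8 | 1.28 | 8.3% | 0.88 |
| 1.0 (stress value) | 2.00 | 16.6% | 0.71 |

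Simulation with N = 210, split 70/140 and 105/105 (20,000 replicates, counts capped at 3 or negative binomial), gave 2.0–2.1%, 4.6–4.7%, 7.7–8.3% and 15.7–16.6%. Robust errors gave 4.6–5.7% over the same SDs and means of 0.5, 0.75 and 1.0.

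**Power for 0.5 against 1.0, N = 210, 2:1 in either direction.**

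| Data | Ordinary errors | Robust errors |
|---|---|---|
| Poisson | 97.7–97.9% | 97.7–97.9% |
| SD 0.6–0.8 | 97.2–99.9% | 96.6–100% |
| SD 1.0 | 94.1–96.4% | 82.9–92.9% |

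The higher power of ordinary errors at SD 1.0 comes from a test that does not hold 5% at a null mean of 0.5.

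**What the SDs imply.** Take three contacts per person, the median the plan cites, each testing positive with probability 1/6. Independent contacts give variance 3 × (1/6) × (5/6) = 0.4167, SD 0.645, φ = 0.833 and size 3.2%. A correlation ρ among one person's contacts multiplies the variance by 1 + 2ρ. The Poisson SD then needs ρ = 0.10, SD 0.8 needs 0.27, and SD 1.0 needs (1.0/0.4167 − 1)/2 = 0.70. The documents give no value for ρ.

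**Clustering.** Network size and intracluster correlation are not given, so no size can be computed. The plan says "A total of 210 individuals (representing a 20% positivity rate among Index Participants"; 0.20 × 1048 = 209.6, about one participant per network.

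**The case against.** The strongest reply is that the plan is silent here, not wrong. It never commits to ordinary errors, and every size above depends on that condition. Its SD range of 0.6 to 0.8 has midpoint 0.7, against a Poisson value of 0.707, and independent contacts would make the test conservative (3.2%). CloseST is the second-aim cohort study, and the C-STRAND primary analysis is untouched. All of this stands and limits the weight of the point. It does not remove it, because a cheap method protects the test on both sides and the named model alone does not.

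A reader might infer three stronger things that the documents do not support:
- That Poisson is contradicted by the planning figures. It is not; the range brackets the Poisson value.
- That the error rate is about 17%. The stress SD of 1.0 is a power input for comparing 0.5 with 1.0, it is exactly Poisson at mean 1.0, and at mean 0.5 it would need a within-person correlation of 0.70.
- That the test is safely conservative whenever the common mean exceeds 0.5. At SD 0.8 that begins only above a mean of 0.64 (0.8² = 0.64; size is 6.9% at 0.55 and 5.8% at 0.60). At SD 1.0 it fails: 9.0% at mean 0.75 and 5.0% at mean 1.0.

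On clustering, the reply is that Network Contacts enter by a narrow route: adults, positive within 14 days, and self-testers must phone in. That also stands, so clustering is a secondary note.

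**Conclusion.** The point holds as an unspecified variance estimator that should be fixed, not as a demonstrated failure of the error rate. If ordinary Poisson errors are used, the nominal 5% test has size of 2.1% to 8.3% across SD 0.6 to 0.8, and the interval runs from 18% too wide to 12% too narrow. This assumes a common mean of 0.5, the same SD in both arms, independent participants and two-sided testing. Network correlation would push towards too many false positives, by an amount that cannot be calculated from the documents and may be small.

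**What to change.** Add to the CloseST paragraph of Data Analysis: the rate ratio is estimated by Poisson regression, with the confidence interval and p-value from robust (sandwich) standard errors; the same applies to the secondary counts. Negative binomial regression is not a substitute, because it cannot represent a variance below the mean, as at SD 0.6.

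Cluster the robust errors on the originating Index Participant where linkage exists: the Index Referral ID in the referral arm, and the QR/URL number shared by an Index Participant's five kits in the self-test arm. Treat unlinked participants as their own cluster and report their number per arm. If no network contributes two participants, this reduces to plain robust errors.

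Plain robust errors cost one sentence and one software option. Power is unchanged if the data are Poisson, about 97% or more at SD 0.6 to 0.8, and about 83% to 93% at SD 1.0. Clustering also needs the QR/URL number recorded at CloseST enrolment. Linkage may stay incomplete in the self-test arm: Ellume kit numbers are not tracked, Network Contacts in CloseST take their own REDCap ID as Referral ID, and people already enrolled may lack the field. The correction for clustering would then be only partial in that arm.

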- Interviewers will try to contact any TR network contact who tests positive about joining the COVID+ cohort, and will keep track of the attempts in REDCap
- The Interviewers will make 4 attempts to reach a COVID+ TR network contact to talk to them about joining the COVID+ cohort
 - The day that the test result is received
 - 1 day following receipt of the test result
 - 2 days following receipt of the test result
 - 7 days following receipt of the test result

- Any ST network contact who tests positive can contact an Interviewer about joining the COVID+ cohort by calling a phone number printed on the bottom of their self-test kit.
- Interviewers will ask if the Network Contact would like to participate in an ongoing study of COVID-19 testing that would provide them with additional self-test kits for close contacts.
- If the COVID-19+ person entered the study through the self-testing arm Index Participant or the Network Contact Scripts J “[Informed Consent for COVID-19+ network contact participant Self-Test arm](#)” and Script K “[Informed Consent for COVID-19+ network contact participant test referral arm](#)”)

If the COVID-19 participant is in the Self-testing arm (COVID-19 ST): (see Script L “[Contact elicitation for COVID-19+ participants ST arm](#)”)

- The interviewer will ask individuals about close contacts and will offer up to 3 additional self-test kits to distribute to close contacts.
- The interviewer will elicit close contact information, and help the individual prioritize who to give testing to.
- The interviewer will instruct COVID-19 participant to tell close contacts to quarantine, monitor symptoms, and that if desired, they can self-test and receive a \$15 card if they do so.
- The interviewer will then conduct the [COVID-19 Participant survey over the phone](#).

Delivery of self-testing kits to close contacts:

Self-test kits can be obtained by pick-up at the PHMC clinic sites where the *Index Participant registered*. Participants should have a contact pick up the additional test kits in their place if they are unable to pick up.

The interviewer will arrange test-kit pick up and will complete the REDCap forms for COVID+ participants.

The interviewer will enter the following key elements:

- Complete COVID-19 participant questionnaire
- Will enter the test kits ID

If the COVID-19 participant is in the test referral arm: (see Script M “[Contact elicitation for COVID-19+ participants TR arm](#)”)

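### CloseST: kit-arm network contacts enter by a different route from December 2021, and neither the Poisson model nor the named confounders include calendar period, so the comparison can be confounded by time

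*Combined protocol and SAP*

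**What the plan says.** **Entry to CloseST, kit arm.** The section on measuring test uptake relies on laboratory data: "We will measure test uptake among self-testers through testing completed at the partner self-testing lab". For the period after the move to Ellume kits, planned for the start of December 2021, the Overview of study says "we will no longer be able to monitor test results from self-testers" and adds: "Self-testers who test positive must contact study staff to be enrolled in the study". The section on verbal consent for the COVID-19 cohort agrees: "Any ST network contact who tests positive can contact an Interviewer about joining the COVID+ cohort".

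**Entry to CloseST, referral arm.** The same section says: "The Interviewers will make 4 attempts to reach a COVID+ TR network contact to talk to them about joining the COVID+ cohort". No dated change to referral-arm case finding is described.

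**Index participants.** Under Randomization, those registered for a COVID-19 test are randomized only after that test. Allocation is 1:1, in permuted blocks stratified by site.

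**Analysis.** Under Data Analysis, "we will use Poisson regression to compare the number of contacts who test positive at week 8 among contacts of SARS-COV-2 positive individuals", by group, with no covariate named. If standardized mean differences above 0.1 show imbalance, additional analyses consider potential confounders. The named examples end with "household size, relationship status, risk of COVID-19 exposure, and site of recruitment". None is enrolment date, calendar period or test type.

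**The concern.** Entry to CloseST comes after randomization: it needs a positive test, contact with staff and consent. For network contacts, the route changed in one arm at one date. If fewer kit-arm network positives enrol afterwards, the kit group holds relatively more early participants than the referral group.

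That matters only if the outcome also differs between the periods. It plausibly could. Community transmission changes over time, and index eligibility was widened in both arms from December 2021, to people whose last positive test was more than 90 days earlier. With both conditions met, a model with group alone attributes part of the period difference to the kits. The main CloseST result would then be shifted in a direction nobody could state in advance.

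**Working it through.** **1. The plan's own figure.** Inputs from Sample Size: means 0.5 and 1.0 (difference 0.5, ratio 2.0), SD 1.0, N = 210, allocation 2:1, alpha 0.05 taken as two-sided.

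- Standardized difference = 0.5 / √(1/70 + 1/140) = 3.416.
- Power = Φ(3.416 − 1.960) = 92.7%, against the stated 93%.
- The stated N = 192 (SD 1.0, 90% power) and N = 54 (SD 0.6, 80% power, t-based) also reproduce.

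The sample size is not in dispute.

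**2. Formula for the spurious ratio.** Let w1 and w0 be the shares of the kit and referral groups that entered before December 2021, and r the ratio of positives per case after versus before. With no arm effect in either period, the crude ratio is

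[w1 + (1 − w1)r] / [w0 + (1 − w0)r].

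It equals 1 if w1 = w0 or if r = 1. Both conditions must fail for bias to arise.

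**3. Assumed inputs.** The documents give none of these:

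- half of index positives occur before December 2021, equally in both arms;
- n network positives join per index positive;
- no kit-arm network positives join afterwards, which is the worst case for the loss;
- r is 2 or 0.5.

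Referral entry is unchanged, so w0 = 0.50. In the kit arm, w1 = 0.5(1 + n) / [0.5(1 + n) + 0.5].

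| Cohort mix | w1 | Ratio, r = 2 | Ratio, r = 0.5 |
|---|---|---|---|
| Index positives only (n = 0) | 0.50 | 1.00 | 1.00 |
| n = 0.5 | 0.60 | 1.40/1.50 = 0.93 | 0.80/0.75 = 1.07 |
| n = 1 | 0.667 | 1.333/1.50 = 0.89 | 0.833/0.75 = 1.11 |
| Extreme: n = 2 kit, 0.5 referral | 0.75 | 1.25/1.50 = 0.83 | 0.875/0.75 = 1.17 |

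Partial retention shrinks the bias: for n = 1 with a quarter of kit-arm network positives still joining, the ratios are 0.92 and 1.08.

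**4. Effect on the test.** For the n = 1 row with N = 210 and period means 0.35 and 0.70 in either order, simulation with robust errors rejects a true null 7–9% of the time at a nominal 5%.

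**5. Would the plan's screen catch it?** For n = 1, the standardized difference in period is (0.667 − 0.50) / √[(0.667×0.333 + 0.50×0.50)/2] = 0.34, above the 0.1 threshold. It would be flagged only if entry date were among the characteristics screened, and even then only for an additional analysis.

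**6. Cost of a period term.** Effective N = N(1 − R²), where R² is the squared correlation of arm and period. For the three affected rows R² is about 0.01, 0.03 and 0.07. Power at N = 210, SD 1.0 becomes 92.5%, 92.0% and Φ(3.416 × √0.93 − 1.960) = 91%. At R² = 0.10 it is 90.0%.

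**The case against.** Four objections carry weight.

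- **The cohort may be mainly index positives.** Sample Size describes the 210 as a 20% positivity rate among index participants (0.20 × 1048 = 209.6). For a cohort of index positives found at enrolment, the mechanism vanishes. This stands and limits the size. It does not remove the point, because positive network contacts are eligible and, since September 2021, index participants may enrol untested.
- **The confounder list is open.** It is introduced as a set of examples, and exposure risk may partly track epidemic phase. A reader might infer that the plan rules out calendar adjustment. It does not: the term is unnamed, not excluded. But nothing commits the sponsor to it, and the primary model stays unadjusted.
- **The loss of kit results is unclear.** The December 2021 update under Self-Collection Test Kits says results reach a study portal when the QR code is used. Delivery of Test Results has staff review all self-test results daily, although its heading covers only index testers and referral-arm contacts. Both sit badly with the Overview. If results are still seen, the shift may be small.
- **A period term can be oversold.** If only a fraction c of kit-arm outcome positives is captured after December 2021, a true ratio of 1 appears as c in that period. With an assumed c = 0.5, the adjusted estimate lies between 0.5 and 1. A main-effect period term cannot repair that.

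A reader might also construct larger biases. Kit:referral entry of 60:30 before and 30:90 after, with rates doubling or halving, gives 0.76 or 1.33. With index positives split 1:1 and referral network positives per index positive constant, that allows at most 80 index positives among 210. It also needs five kit-arm network positives per index positive before the change and none after. That sits poorly with a target derived from index positives.

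**Conclusion.** The point holds as a risk that a low-cost prespecification would reduce. The documents establish the arm-specific change in how network contacts enter, the absence of any described change in the referral arm, and the absence of a calendar term. They do not establish that confounding occurs. A reader might infer that the arm mix must change and that epidemic phase does bias the result, but that requires period counts and period rates, and the documents report neither.

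Under the stated assumptions the spurious ratio is about 0.89–0.93 or 1.07–1.11, and 0.83 or 1.17 at the extreme. It is 1.00 for index positives alone or for equal rates across periods. This is small to moderate against a planned ratio of 2.0. The randomized C-STRAND comparison is not touched by this mechanism, since its allocation is 1:1 throughout.

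**What to change.** In the CloseST part of Data Analysis:

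1. Put calendar period of CloseST entry in the primary Poisson model as a fixed term, whatever its standardized difference: at least before versus from December 2021, preferably calendar quarter. Name it in the confounder list.
2. Report participants and positive contacts by arm and period, with an arm-by-period check.
3. Add a sensitivity analysis limited to index positives.
4. State that the period term does not correct kit-arm self-selection, arm-specific outcome capture after December 2021, or the change from PCR to antigen kits.
5. Reconcile the Overview of study with the Self-Collection Test Kits update and Delivery of Test Results on whether kit results are monitored.

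The cost is a few sentences and one or a few degrees of freedom. Entry requires a positive test in the past 14 days, so the dates must already be known. Power falls by about 1 to 3 points over the R² range shown, and by more only if the arm mix shifts strongly, which is when the adjustment matters most.
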